9.7.2. Multiple Testing in Adaptive Seamless Design

9.7.2.1 Combination Test

Confirmatory testing of the hypothesis comparing optimal dose with placebo using data collected from Phase II and Phase III part will use a closed testing procedure. This hypothesis will be rejected at level α (one-side 0.025) if it and all intersection hypotheses involving it are all rejected at local level α (one-side 0.025). The testing strategy used to combine results from Phase II and Phase III part will be a combination test based on the inverse normal weighting method, with the test statistic of the combination test calculated as (*Bauer and Kohne 1994*):

$$\text{Sqrt}(n_1/n)*\Phi^{-1}(1-p_1) + \text{Sqrt}(n_2/n)*\Phi^{-1}(1-p_2)$$

Where n_1 and n_2 are the sample size in Phase II and III, respectively, $n = n_1+n_2$, Φ refers to the standard normal distribution, and p_1 and p_2 are the p -value from Phase II and III, respectively. p_1 is the Simes-adjusted p -value in Phase II, and p_2 is the unadjusted p -value to compare optimal dose with placebo in Phase III.

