- The 1st interim analysis is for safety evaluation. Only safety data will be reviewed at the 1st interim analysis. The IDMC may request to review efficacy data if early data warrants. Decision s from the IDMC will take the nature of premature data into account unless prevailing data suggest conclusive outcome of the trial. Early safety signal will guide patient enrollment to maximize the effectiveness of treating this patient population with SCTA01.
- The 2nd interim analysis is for dose selection: the analysis will be performed at the end of Phase II when the 285th patient completed Day 29 or Early Withdraw visit. The dose selected to continue to the Phase III part will be the dose with the greater effect in reduction of viral load compared to placebo at Day 8. Time to clinical improvement of each dose will be evaluated and the RR threshold of 1.15 will be used as a futility boundary at the end of Phase II. The futility boundary is non-binding, and the IDMC may recommend study continuation

even if the futility bound is met on TTCI. If any safety signal is observed for any dose, the IDMC will weigh this information against the efficacy results in selecting the dose for Phase III.

- The 3rd interim analysis is the penultimate analysis that allows for stopping for superior efficacy. It is planned when 160 patients in Phase III (approximately 31% information time of Phase III part, which will have approximately 128 TTCI events) have been documented in the ITT population. If the interim analysis is performed at 31% of information time of Phase III, based on Pocock type boundary of α -spending function, a 1-sided p -value less than 0.01068 using inverse normal method to combine p -value from Phase II part and Phase III part will need to be observed to declare statistical significance. A futility boundary of an observed RR of 1.22 will be used to declare failure of the study when TTCI events from Phase II and Phase III part combined are exactly 280, which is equivalent to an observed one-sided p -value of 0.05.

Note: The critical values of nominal p -value and hazard ratio that will be used to declare statistical significance and/or futility at the interim analysis will be calculated based on the actual number of the TTCI events documented at the time the interim analysis.

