9.3. Statistical Decision Rules

A combined *p*-value using inverse normal method of less than 1-side of 0.01068 from 3rd interim analysis or less than 1-side of 0.0166 from final analysis will need to be observed to declare statistical significance. The total number of patients in the ITT analysis sets for primary analysis will include patients in the recommended dose group in Phase II and in the same dose group that continued in Phase III, or the control group. i.e., 95 + 255 = 350 patients for recommended dose group or for control group. The patients from the inferior dose group (95 patients) in Phase II will only contribute to the multiplicity penalty of dose selection.

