9.4. Sample Size

The treatment estimates are based on the study ACTT-1 of Remdesivir[®] for COVID-19. Under the TTCI definition used in this study, rate ratio (RR) for recovery for the severe patients, the patients with 5-point of baseline ordinal score and the patients with 6-point of baseline ordinal score is 1.31, 1.45 and 1.09 respectively^{31,32}. The event rate for the patients with 5-points is 88.8% and 76.8% for Remdesivir[®] group and placebo group, respectively. The assumption to calculate the sample size is set on the results from 5-points patients, which is RR as 1.4 and event rate as 80%. The sample size determination assumptions aim at a more meaningful clinical difference under a stricter TTCI definition.

Sample size is calculated based on the following assumptions:

- Overall Type-I error rate should not exceed 2.5% (1-sided);
- Rate ratio (RR) sets to be 1.4 (if the median TTCI is 9 days on the placebo group, the SCTA01 group will be 6.5 days under the assumption of Exponential distribution);
- Randomization ratio of study drug group and placebo group in Phase III is 1:1;
- Randomization ratio of medium dose group, high dose group and placebo group in Phase II is 1:1:1;
- 80% event rate;
- Sample size ratio of Phase II and Phase III is 1:1.79;
- Simes method will be applied to attain adjusted *p*-value from Phase II;

- Inverse normal weighting method will be used to combine *p*-value from Phase II and Phase III part;
- The 3rd interim analysis, which is the penultimate analysis for superior efficacy stopping and futility analysis, will be conducted when 31% of the TTCI events have been observed from the Phase III part;
- Pocock boundary (Lan DeMets 1983) will be used to control overall Type I error within 1-sided 2.5%;
- The critical values of nominal *p*-value will be re-calculated based on the actual number of TTCI events documented at the time of interim analysis and final analysis.

The study will randomize 795 patients totally, with Phase II of 285 patients and Phase III of 510 patients (255 in each group), providing over 90% power.

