9.7.2.2 Adaptive Combination Test

We will control family-wise error rate at a nominal one-sided α of 0.025, which is the probability of rejecting at least one true null hypothesis. The general principle of “adaptive combination test” will be adhered to. Independence of the test statistics from Phase II and Phase III is achieved by fixing the follow-up time to obtain events required for the efficacy analysis for each Phase, thereby ensuring control of the Type I error via the closure principle.

To determine the efficacy boundary for the interim analysis, the critical values of the Pocock boundary is calculated using the sample sizes in the Phase III part alone. This then provides a conservative boundary to control the family-wise Type I error rate better than 2.5% when these boundaries are compared to the p -values derived from combining the p -values from the Phase II and Phase III parts. The boundaries are conservative when the same weights are used for both the interim and final p -values because when the same weights are used, the correlation between the p -values at interim and final is stronger when the p -values are first combined with the same data from phase II than when they are not combined with the Phase II data. Therefore, the adjustment of the final alpha required to control the Type 1 error overall would be smaller and the process is guaranteed to protect against Type I error inflation. This conclusion is supported by simulation results demonstrating that under the null hypothesis, the Type I error rate is less than 2.5%³³⁻³⁶.

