Interim 1(Safety review only)	NA	NA	NA	NA	NA
End of Phase II	149	NA	RR < 1.15	0.9385	0.8106
Interim 3	280	0.01068	RR < 1.22	0.9987	0.985
End of Phase III	556	0.0166	NA	0.9999	0.9897

Our simulation results suggest with the planned sample size and timing of interim analysis, under the hypothesis that SCTA01 is harmful (RR = 0.9) or has no effect (RR = 1), the probability of stopping the trial for applying a futility boundary of RR=1.15 is very probable with at least 81% probability, even at the early enrollment of the trial, e.g. the end of Phase II. Similarly, the probability of stopping the trial for applying a futility boundary of RR=1.2 is very probable with at least 88% probability.

Phase III: An unblinded interim analysis is planned.

The penultimate analysis, that allows for stopping the study for superior efficacy is planned when approximately 128 (31%) of the TTCI events have been documented in the Phase III ITT population. An α -spending function due to Lan DeMets (1983) with Pocock type stopping boundary will be used for the interim efficacy analysis. Therefore, if the interim analysis is done right after 280 events from Phase II and Phase III part have been documented, the combined *p*-value based on the inverse normal method of less than **1-side of 0.01068** will need to be observed to declare statistical significance. A futility boundary of an observed RR of 1.22 may be used to declare failure of the study when TTCI events from Phase II and Phase III part combined are exactly 280. Similarly, this more stringent than calculated futility boundary is set to control unwanted false positive rate. Note that the critical values of nominal *p*-value and hazard ratio needed to declare statistical significance at the interim analysis will be calculated based on the actual number of TTCI events documented at the time of the interim analysis.

An independent statistician external to the study team will perform the interim analyses and present the results to the IDMC. The IDMC will provide the Sponsor with a recommendation to continue the trial as planned, to have an interruption, to make a protocol amendment, or to terminate the trial. If the interim analysis demonstrates significant shorten TTCI in SCTA01 group compared to control group, the IDMC could recommend to terminate and un-blinded the study, and thus announce the study as completed.

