9.7.6. Final Analysis

Final analysis will be performed when 556 TTCI events have been observed. A combined *p*-value based on the inverse normal weighting method of less than **1-side of 0.0166** will need to be

observed to declare statistical significance. The above derived boundaries are based on the assumption that the final analysis is performed when exactly 556 events are observed from both Phase II and Phase III part. If this assumption does not hold, the boundaries for *p*-value will be re-calculated according to the aforementioned α -spending function.

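### Does the undefined 'Simes-adjusted' Phase II p-value in 9.7.2.1 leave the closed test incomplete?

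*Combined protocol and SAP*

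**What the plan says.** Section 9.7.2.1 sets out a closed test for the selected dose against placebo at one-sided 0.025. The hypothesis is rejected only "if it and all intersection hypotheses involving it are all rejected at local level" α. One inverse normal statistic follows, with weights from the two sample sizes. Its Phase II input "is the Simes-adjusted" p-value; its Phase III input is the unadjusted p for the selected dose. Section 9.4 only names the method ("Simes method will be applied to attain adjusted").

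Section 9.3 limits the role of the dropped dose: "The patients from the inferior dose group (95 patients) in Phase II will only contribute to the multiplicity penalty of dose selection". Section 9.7.2.2 defines the family-wise error as the chance of rejecting any true null hypothesis and describes its design as "thereby ensuring control of the Type I error via the closure principle".

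The thresholds are worded for one combined p-value: "based on the inverse normal method of less than" 0.01068 at the third interim (9.7.5) and "based on the inverse normal weighting method of less than" 0.0166 at the final analysis (9.7.6).

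Under 3.1 the dose carried forward "will be the dose with the greater effect in reduction of viral load compared to placebo at Day 8". Time to clinical improvement (TTCI) of each dose is also evaluated.

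**The concern.** With two doses, closure needs two combinations: one for the intersection (neither dose works) and one for the selected dose alone. The plan writes out one formula and one threshold per look. A programmer who inserts the ordinary Simes p, min(2 × smaller p, larger p), and checks only that combined p has tested the intersection and nothing else.

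This would not matter if the dose with the better TTCI result were always selected. Here selection is led by Day 8 viral load, so the selected dose may have the larger Phase II TTCI p. A small p from the dropped dose would then pull the Simes p down and credit the selected dose with evidence it did not produce. That contradicts 9.3 and would undo the error control claimed in 9.7.2.2. Simulating only the case where both doses are null would not show it.

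**Working it through.** **Inputs.** Phase II: three arms of 95. Phase III: 510 patients (9.4). Events: 149 at the end of Phase II, 280 pooled at the third interim, 556 at the end (Table 7), so Phase III contributes 280 − 149 = 131 and then 556 − 149 = 407. The plan does not say whether n1 counts all 285 Phase II patients or the 190 in the two compared arms, so both were run: n1/n = 285/795 = 0.358 or 190/700 = 0.271. Assumed: correlation 0.5 between the two Phase II z-scores (shared placebo), and the dropped-dose rate ratio (RR).

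**The plan's own boundaries.** Pocock-type spending at t = 0.31 gives 0.025 × ln(1 + (e − 1) × 0.31) = 0.010675, against 0.01068 stated. The final boundary, from a bivariate normal with correlation √t, is 0.01660 at t = 160/510, against 0.0166 stated. Both reproduce.

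**What closure requires.** Let p_s and p_d be the Phase II TTCI p-values of the selected and dropped doses.
- Intersection: Phase II input S = min(2 × smaller, larger).
- Selected dose alone: Phase II input p_s. (Simes applied to a single hypothesis returns its own p.)
- The Phase III p is common to both, and the statistic falls as the Phase II input rises. Both combinations therefore cross exactly when the one using max(p_s, S) crosses. A single combined p can thus carry the whole closed test.

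**When the two uses differ.** If p_s is the smaller, S = min(2p_s, p_d) is never below p_s, and they agree. If p_s is the larger, S = min(2p_d, p_s), and they differ only when 2p_d < p_s.

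**Example.** Take p_s = 0.15, an observed RR of exp(2 × 1.036/√149) = 1.19, and p_d = 0.01. Then S = 0.02 and max(p_s, S) = 0.15. The Phase III z needed at the final analysis is (2.130 − √(n1/n) × z1)/√(n2/n), where z1 is the normal quantile of the Phase II input.

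| n1 | Phase II input | z needed | Phase III p needed | Phase III RR |
|---|---|---|---|---|
| 285 | 0.02 | (2.130 − 0.599 × 2.054)/0.801 = 1.12 | 0.131 | 1.12 |
| 285 | 0.15 | (2.130 − 0.599 × 1.036)/0.801 = 1.88 | 0.030 | 1.20–1.21 |
| 190 | 0.02 | (2.130 − 0.521 × 2.054)/0.854 = 1.24 | 0.107 | 1.13 |
| 190 | 0.15 | (2.130 − 0.521 × 1.036)/0.854 = 1.86 | 0.031 | 1.20 |

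This example passes the 1.15 Phase II bound but would stop under the optional stricter bound of 1.2 that 9.7.5 mentions.

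**Error rates.** 2,000,000 simulated trials per case, conditional on a null dose being carried forward. Ranges cover n1 = 190 to 285. An efficacy crossing at the third interim takes precedence over futility.

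| Dropped-dose RR (assumed) | Rule | No futility stop | 1.15 and 1.22 obeyed | 1.2 and 1.22 obeyed |
|---|---|---|---|---|
| 1.4 | Ordinary Simes alone | 15.7–19.1% | 3.5–4.5% | 2.7–3.4% |
| 1.2 | Ordinary Simes alone | 6.3–7.1% | 1.8–2.2% | 1.5–1.8% |
| 1.0 (both null) | Ordinary Simes alone | 2.2% | below 2.2% | below 2.2% |
| Any of these | Full closed test | at most 2.4% | at most 2.4% | at most 2.4% |

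**Against the text.** Using ordinary Simes alone omits the first requirement of the closure sentence in 9.7.2.1, that the selected-dose hypothesis itself be rejected. It also lets the dropped dose help where 9.3 allows it only to penalise. Using max(p_s, S) satisfies 9.3, 9.7.2.1 and 9.7.2.2 together.

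**The case for a change.** The strongest case for a change is that this is the confirmatory primary test and its key input has no formula. Sections 9.3, 9.7.5 and 9.7.6 all speak of one combined p, so a literal programmer could test only the intersection. The futility bounds are no reliable protection: the Phase II bound is non-binding, and 9.7.5 lets the committee continue on a viral-load effect. Leaving the term open until Phase II data exist would also allow a choice between the two uses just when they differ. One defining sentence would settle it.

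The arithmetic in that case stands, and so does the observation that the term is undefined. What does not stand is treating ordinary Simes alone as a permitted reading. The formula follows directly on the closure sentence and can be read as the local test for each hypothesis in the closure. Applied that way, it is the full closed test. The feared choice is not open either, because one of the two options breaks a rule already fixed in writing. A defining sentence would be tidier, but it would restate that rule and leave boundaries, weights and decisions as they are.

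The large figures also need several things together: departure from 9.7.2.1, one inert dose beside one at the full design effect, the inert dose leading on viral load, and every futility bound overridden. They are conditional rates. The family-wise error multiplies them by the chance that the inert dose is selected, which the documents do not give, and Section 2.9 expects that efficacy may not depend on dose.

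**Conclusion.** The concern does not call for a change. The plan leaves a term undefined, but its own closure rule, its limit on the dropped dose and its family-wise claim all lead to one implementation: the Phase II input is the larger of the selected dose's own p and the Simes p. With the stated boundaries the error is then at most 2.4% one-sided in the null cases run, within 2.5%. The inflated rates (15.7–19.1% with no futility stop, 3.5–4.5% with the 1.15 and 1.22 bounds obeyed, at an assumed dropped-dose RR of 1.4) describe a departure from the plan. This is a gap in detail that an analyst following 9.7.2.1 fills correctly. The conclusion rests on the closure sentence being carried out in full, on fixed weights (either n1 gives the same answer), and on the correlation of 0.5 from the shared placebo arm.

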9.7.2.2 Adaptive Combination Test

We will control family-wise error rate at a nominal one-sided α of 0.025, which is the probability of rejecting at least one true null hypothesis. The general principle of “adaptive combination test” will be adhered to. Independence of the test statistics from Phase II and Phase III is achieved by fixing the follow-up time to obtain events required for the efficacy analysis for each Phase, thereby ensuring control of the Type I error via the closure principle.

To determine the efficacy boundary for the interim analysis, the critical values of the Pocock boundary is calculated using the sample sizes in the Phase III part alone. This then provides a conservative boundary to control the family-wise Type I error rate better than 2.5% when these boundaries are compared to the p -values derived from combining the p -values from the Phase II and Phase III parts. The boundaries are conservative when the same weights are used for both the interim and final p -values because when the same weights are used, the correlation between the p -values at interim and final is stronger when the p -values are first combined with the same data from phase II than when they are not combined with the Phase II data. Therefore, the adjustment of the final alpha required to control the Type 1 error overall would be smaller and the process is guaranteed to protect against Type I error inflation. This conclusion is supported by simulation results demonstrating that under the null hypothesis, the Type I error rate is less than 2.5%³³⁻³⁶.

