- Chemistries, hematology, urinalysis, coagulation test, IL-6, ferritin, procalcitonin, thrombin time, D-dimer (Phase II, III);
- Number and proportion of patients who are suspected to experience ADE (Phase II, III).

- Virologic efficacy of SCTA01:

- Change from baseline in viral shedding as measured by quantitative reverse transcription polymerase chain reaction (RT-qPCR) in NP or OP swab samples (Phase II, III);
- Time-weighted average change from baseline between SCTA01 group and placebo group in viral shedding as measured by RT-qPCR in NP or OP swab samples (Phase II, III);
- Time to SARS-CoV-2 RNA negative (NP or OP swab samples) as determined by RT-qPCR (Phase II, III).

- Pharmacokinetics (PK) of SCTA01:

- Pharmacokinetic characteristics in severe COVID-19 patients (Phase II).

- Immunogenicity of SCTA01:

- Immunogenicity assessment includes the number and percentage of subjects who develop detectable anti-drug antibodies (ADA) (Phase II, III).

Exploratory Endpoints:

- The correlation between the baseline serological antibody level and therapeutic effect (Phase II, III);
- Quantitative SARS-CoV-2 virus in patient's blood (Phase II, III).

Study Design:

The study is a multicenter, adaptive, randomized, double-blinded and placebo-controlled Phase II/III trial, and will be conducted at selected investigational sites globally. The study is comprised of 2 parts: dose selection (Phase II) and pivotal treatment effect (Phase III).

Phase II part will evaluate the efficacy, safety and PK of SCTA01 15 mg/kg and 50 mg/kg in severe patients with COVID-19. The primary endpoint will evaluate the difference of TTCI among study group 1 [SCTA01 15 mg/kg + best supportive care (BSC)], study group 2

(SCTA01 50 mg/kg + BSC) and control group (placebo + BSC) up to Day 29. The secondary endpoint will evaluate the difference of virologic efficacy among study group 1 (SCTA01 15 mg/kg + BSC), study group 2 (SCTA01 50 mg/kg + BSC) and control group (placebo + BSC) from baseline to Day 8, and then determine the recommended dose of Phase III part.

In the Phase II part of the study, 285 subjects will be randomized by 1:1:1 ratio to 15 mg/kg group, 50 mg/kg group and placebo group, with 95 subjects in each group.

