9. STATISTICAL METHODS

9.1. General Principle

All statistical analyses will be done with the SAS software Version 9.4 or later. This is a double-blind, placebo controlled randomized trial with a one-sided Type I error rate of 0.025. Continuous variables will be summarized using descriptive statistics. Categorical variables will be summarized using frequency counts and percentages of patient incidence.

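### The final efficacy level of 0.0166 is set from Phase III alone, leaving about 0.0012 to 0.0017 of the one-sided 0.025 unspent; about 0.018 would use it, once the combination weights are stated

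*Combined protocol and SAP*

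**What the plan says.** The trial is run at a "one-sided Type I error rate of 0.025" (Section 9.1). Section 9.7.2.1 combines the Simes-adjusted Phase II p-value with the unadjusted Phase III p-value by the inverse normal method. The weights are the square roots of n1/n and n2/n, where n1 and n2 "are the sample size in Phase II and III, respectively". Section 9.3 sets the one-sided levels for the combined p-value at 0.01068 (3rd interim) and 0.0166 (final).

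Section 9.7.2.2 explains where those levels come from: "the critical values of the Pocock boundary is calculated using the sample sizes in the Phase III part alone". It adds that using the same weights at both looks makes the combined p-values more strongly correlated than the Phase III ones, that the final adjustment could therefore be smaller, and that the boundary is conservative. Sections 9.4 and 9.7.6 provide for recalculating the levels at the actual event counts.

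On the sample sizes behind the weights, Section 9.4 states "Sample size ratio of Phase II and Phase III is 1:1.79", while Section 9.3 states "The patients from the inferior dose group (95 patients) in Phase II will only contribute to the multiplicity penalty of dose selection".

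**The concern.** A group-sequential boundary should use the joint distribution of the statistics that are tested. Here the tested statistics are combinations sharing one Phase II term, whereas 0.0166 is solved as if only Phase III data were compared at the two looks. With fixed weights the correct correlation is known in advance, so the stricter level is not needed for error control and part of the allowed alpha goes unused.

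The weights also need an explicit statement. The definition in Section 9.7.2.1 and the ratio in Section 9.4 imply n1 = 285, all three Phase II arms. Section 9.3, and the 149 and 556 events in Table 7, point to n1 = 190, the selected dose plus placebo. At stake are a small amount of power and a test statistic that two statisticians could compute differently from the same text.

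**Working it through.** **Inputs.** One-sided alpha 0.025 (9.1); Phase II 285 patients, 95 per arm, and Phase III 510 (synopsis, 3.1); interim at 31% of Phase III events (9.4); event rate 80% and design RR 1.4 (9.4); levels 0.01068 and 0.0166 (9.3).

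**Step 1: reproduce the plan's levels.** Pocock-type spending at t = 0.31 gives 0.025 × ln(1 + (e − 1) × 0.31) = 0.010675, which is the stated 0.01068. Using the Phase III correlation √0.31 = 0.557, the final level that brings the total to 0.025 is 0.01666, or 0.0166 truncated. At t = 160/510 = 0.3137 it is 0.01660. The combined fraction 280/556 would instead give 0.0156 and 0.0138. The stated pair therefore does come from Phase III alone.

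**Step 2: correlation of the tested statistics.** The interim statistic is w1·Z(II) + w2·Z(III, interim) and the final one is w1·Z(II) + w2·Z(III, final). Their correlation is w1² + w2²·√t.

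| | n1 = 285 | n1 = 190 |
|---|---|---|
| w1² | 285/795 = 0.358 | 190/700 = 0.271 |
| w2² | 510/795 = 0.642 | 510/700 = 0.729 |
| correlation | 0.358 + 0.642 × 0.557 = 0.716 | 0.271 + 0.729 × 0.557 = 0.677 |
| spent by 0.01068 / 0.0166 | 0.0233 | 0.0238 |
| unspent | 0.0017 | 0.0012 |
| final level that spends 0.025 | 0.0185 | 0.0180 |

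These figures treat the Phase II p-value as uniform under the null. Simes makes the procedure more conservative still.

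**Step 3: which n1.** 510/285 = 1.79, the ratio in Section 9.4; 510/190 = 2.68. On the other side, 190 × 0.8 = 152, close to the 149 events in Table 7, and 149/556 = 0.268 is close to 190/700 = 0.271. The plan never writes n1 as a number, so 285 is an inference.

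**Step 4: power and error by simulation.** The simulations use 152 Phase II events, 128 Phase III events at the interim and 408 at the end. The log-rank statistic is taken as normal with variance 4/events on the log rate ratio scale, and the two Phase II comparisons have correlation 0.5. The Phase II p-value is the larger of the Simes p-value and the selected dose's own p-value. The effect of the other dose and the selection rule are not in the documents and were varied.

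- *Threshold change only, weights kept at 285:510.* No futility stops: +0.2 to +0.4 points at RR 1.4 and +0.9 to +1.1 at RR 1.3. With futility stops: about +0.1 to +0.5.
- *Threshold and weights both changed to 190:510.* No futility stops: +0.2 to +1.1 points at RR 1.4, and up to +2.4 at RR 1.3 (76.5% to 78.9%, other dose inert and the active dose always chosen). For that last setting the gain is 0.6 with the RR 1.22 bound alone (64.5% to 65.1%) and 0.1 with both bounds (59.8% to 59.9%).
- *Weights changed alone, level kept at 0.0166, both bounds enforced.* Power falls by about 0.1 to 0.4 points (for example 61.0% to 60.6% at RR 1.3, both doses active).
- *Both doses null, no futility stops.* Under the plan the error is 1.6% (dose chosen independently of TTCI) to 2.2% (better-TTCI dose chosen). With the revised threshold it is at most about 2.3%.

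**The case against.** The plan has not overlooked anything. Section 9.7.2.2 names the stronger correlation, gets its direction right and accepts the conservatism. A reader might infer from Steps 1 and 2 that the boundary is an error or that Type I error is at risk. The documents support neither: this is a disclosed, prespecified choice on the safe side. That stands, and it limits the point to efficiency and clarity.

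A reader might also infer that a Phase II weight including the dropped arm is wrong. Any prespecified weights are valid, and the Simes p-value does use all three arms. If both doses work, pooling them against placebo gives Phase II information of 190 × 95/285 = 63.3 against 255 × 255/510 = 127.5 in Phase III. That is a share of 63.3/190.8 = 0.33, nearer to 0.358 than to 0.271. The weights are clearly inefficient only when the other dose is inert. This also stands, so changing them is a trade-off; only stating them is needed.

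Finally, the gain is small and depends on futility. The end-of-Phase-II bound is non-binding. For the RR 1.22 bound at the 3rd interim, the synopsis and Section 3.1 say it will be used and Section 9.7.5 says it may be. With bounds enforced, little of the gain remains. The threshold change still cannot lose power, because with the weights held fixed it only enlarges the rejection region.

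**Conclusion.** The point holds as a modest efficiency and clarity issue. The stated levels reproduce from Phase III alone and spend 0.0233 (285:510) or 0.0238 (190:510) of the 0.025, before Simes. Recovering the remainder moves the final level from 0.0166 to about 0.0185 or 0.0180.

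The plan's claim of "providing over 90% power" at the design value ("Rate ratio (RR) sets to be 1.4") is not in question: without futility stops, simulated power under the plan is 92.3% to 97.5%. A reader might take the 2.4-point gain at RR 1.3 as the cost of the plan. It is a favourable case that needs an effect below the design value, an inert second dose that is never selected, a change of weights as well as of threshold, and no futility stop. RR 1.3 is still a reasonable scenario, since Section 9.4 reports 1.31 for severe patients in the reference remdesivir trial.

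The alpha figures depend only on the weights and t = 0.31. The power figures also depend on the assumed effect of the other dose, the selection rule, the normal approximation and the correlation of 0.5.

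**What to change.** Before Phase II unblinding, amend the SAP and Sections 9.3, 9.4, 9.7.2 and 9.7.6, with Table 7, to:

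1. State n1 and n2 as numbers and make the sections agree. The choice must not depend on Phase II results.
2. Keep 0.01068 at the 3rd interim.
3. Solve the final level from the correlation w1² + w2²·√t, with t the Phase III information fraction at the interim. As planned this gives about 0.0185 (n1 = 285) or 0.0180 (n1 = 190), recomputed at the actual event counts.

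Moving the weights to 190:510 is optional. It helps if the other dose is inert and no futility stop is applied, and does not help if both futility bounds are enforced.

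The cost is SAP wording and a few lines of code, with no added patients, visits or alpha; recalculation at actual events is already planned. The documents do not show whether any unblinded look had taken place by version 5.0, so the sponsor should record that the change was made without access to unblinded Phase II data.
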